1.0 Study Summary

Study Title	Objective Assessment of Pain Thresholds in Women with Vulvodynia
Study Design	Clinical Trial
Primary Objective	Develop annotated pain maps showing region and size of area sensitive to mechanical stimulus. The pain maps will be created by combining IR images, photographs, and clinical input, and will be correlated with patient co-morbidities.
Secondary Objective(s)	a-Determine changes in the location and size of sensitive regions following various conventional clinical interventions for vulvodynia. b-Develop a large, information-rich database of annotated pain maps from patients, and use Artificial Intelligence to identify patterns and trends.
Research Intervention(s)/ Investigational Agent(s)	Infrared imaging of the vulva and assessment of pain intensity using cotton-tipped swab.
IND/IDE #	N/A
Study Population	Women with vulvodynia and healthy controls
Sample Size	60 women (30 in each group)
Study Duration for individual participants	One day 1 hour

Study Specific Abbreviations/ Definitions	
--	--

2.0 Objectives*

2.1 *Describe the purpose, specific aims, or objectives of this research.*

Response:

We have been developing a novel medical technique for the diagnosis and classification of vulvodynia. The technique will quantitatively quantify the magnitude and location of areas of sensitivity to touch/pressure and simultaneously use thermal and photo imaging to identify regions of inflammation. The technique builds on current methodology used in assessment and knowledge about the known pathophysiology of the disorder. For this aspect of study, we will assess thermal indicators of inflammation with an infrared camera and subjective pain sensitivity with traditional methods. Through this combination of measurements, we plan to expand the diagnostic tools used in patient care as well as on the classification of this heterogeneous disorder. Specific aims include developing annotated pain maps that show regions of sensitivity and changes in temperature; determining changes in the above parameters during and after traditional medical treatment for the condition; and developing a large database of annotated pain maps for use with artificial intelligence to identify patterns and trends which will be correlated with clinical outcome data.

2.2 *State the hypotheses to be tested, if applicable.*

NOTE: A hypothesis is a specific, testable prediction about what you expect to happen in your study that corresponds with your above listed objectives.

Response:

Women with vulvodynia will show specific patterns of pain sensitivity and inflammatory changes (identified by thermography) compared to women without vulvar pain.

3.0 Scientific Endpoints*

3.1 *Describe the scientific endpoint(s), the main result or occurrence under study.*

NOTE: Scientific endpoints are outcomes defined before the study begins to determine whether the objectives of the study have been met and to draw conclusions from the data. Include primary and secondary endpoints. Some example endpoints are: reduction of symptoms, improvement in quality of life, or survival. Your response should not be a date.

Response:

Thermographic evidence of inflammation in the areas of pain sensitivity in women with provoked vulvodynia compared to normal controls.

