5.0 Study Design*

5.1 *Describe and explain the study design (e.g. case-control, cross-sectional, ethnographic, experimental, interventional, longitudinal, observational).*

Response:

Prospective study of women with vulvodynia and normal controls. We plan to evaluate a novel technique that quantifies both pain intensity and records thermographic changes of the vulva in women with a clinical diagnosis of provoked vulvodynia and normal controls. The study subjects will have a new or prior diagnosis of provoked vulvodynia and will be invited to participate in this evaluation. Women with prior diagnosis of vulvodynia will be symptomatic and untreated at the time of assessment. Control subjects will be unaffected women presenting for routine care who do not have vulvar pain or other active vulvar or vaginal disorder as these may interfere with thermographic mapping.

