19.0 Data Management and Analysis*

19.1 *Describe the data analysis plan, including any statistical procedures. This section applies to both quantitative and qualitative analysis.*

Response: Both visible and infrared images will be acquired using our state-of-the-art FLIR E-95 camera. The E-95 is one of the best IR cameras available. It has very high spatial resolution and temperature sensitivity. In summation: if there is any correlation between temperature and vulvodynia, this camera will be able to see it. The camera's software stores both of these images along with metadata in a single jpeg. We have already designed our own custom software to extract the raw temperature data from these files. Our software will control the camera remotely through a USB link. This, along with mounting the camera on a tripod, will ensure that there is minimal "smearing" of the image due to small uncontrollable movements of the person operating the camera. This will give us the highest accuracy possible. In addition, our graphical software interface will allow the user to mark the image to indicate where sensitivity to pressure or an increase in thermal activity was observed. As we expect spatial variation in temperature from the affected area to the unaffected, we will provide the user with a variety of options for subtracting the average body temperature to make the difference more visible. All data will be stored securely to maintain patient confidentiality. Once we have collected enough data, we can begin the process of establishing the metrics by which we can diagnose the patients. Considering all of our data (pressure, temperature, color (from visible light image)) we can determine the connection of each to a positive diagnosis and assign a finally probability to our result.

19.2 *If applicable, provide a power analysis.*

NOTE: This may not apply to certain types of studies, including chart/records reviews, survey studies, or observational studies. This question is asked to elicit whether the investigator has an adequate sample size to achieve the study objectives and justify a conclusion.

Response: This is a pilot study. No power analysis will be performed.

19.3 *Describe any procedures that will be used for quality control of collected data.*

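### The only endpoint names no region for controls and no temperature measure, and no masked or locked reading is stated; one comparison at matched loci would reduce the risk cheaply.

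*Combined protocol and SAP*

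**What the plan says.** Section 3.1 states one endpoint: "Thermographic evidence of inflammation in the areas of pain sensitivity in women with provoked vulvodynia compared to normal controls". Under section 5.1, "Control subjects will be unaffected women presenting for routine care who do not have vulvar pain".

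Section 12.1 sets the order of work. Step A takes images and thermographic readings before any contact except placing the drape. Step B scores swab pain from 0 to 10 at predetermined loci and adds the scores to the thermal map; it is not limited to cases. Step C compares the two measures away from the visit and names no statistic. Section 14.1 places the analysis in a separate laboratory and has de-identified data shared.

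Section 19.1 describes three uses of the images:
- Raw values: "We have already designed our own custom software to extract the raw temperature data from these files".
- Marking: the user can "mark the image to indicate where sensitivity to pressure or an increase in thermal activity was observed".
- Subtraction: "we will provide the user with a variety of options for subtracting the average body temperature to make the difference more visible".

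It adds: "Once we have collected enough data, we can begin the process of establishing the metrics by which we can diagnose the patients". Section 19.2 states: "This is a pilot study. No power analysis will be performed". Section 1.0 gives pain maps as the primary objective and 30 women per group.

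**The concern.** A case-control comparison of temperature needs the same anatomical region in both groups, one defined measurement, and a reading that cannot follow the group label or the pain score. Section 3.1 defines the region by pain, which controls are selected not to have. Section 19.1 leaves open whether the endpoint uses raw temperature, subtracted temperature or a user's mark. Once swab scores are on the thermal map, anyone who places regions or marks heat on it can see where the woman hurt.

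If some loci are naturally warmer and also tend to be the painful ones, an unmatched comparison shows heat in cases when there is none. Averaging over all loci avoids that bias but dilutes a real local effect. In a pilot, either result would pass into the diagnostic metrics and the image database that the protocol plans to build.

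**Working it through.** **No plan figure to reproduce.** The 60 women come without effect size, SD, alpha or test.

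**Inputs.** From the protocol: 30 v 30. Assumed: two-sided 5%, total SD 1, L = 4, 6 or 8 loci, two painful loci per case, within-woman correlation r = 0.5 or 0.8, and two loci 0.3 SD warmer in every woman. Painful loci are the same two warm loci in every case, or favour those two 3 to 1, or are spread evenly. That makes 18 settings, each simulated 10,000 times with a Welch test.

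**Region, no true difference.** Compare painful loci in cases with the mean of all loci in controls. When the two warm loci hurt in every case:

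- Bias = 0.3 × (1 − 2/L) = 0.15, 0.20 and 0.225 SD for L = 4, 6 and 8.
- Variance of a mean of m loci = r + (1 − r)/m.
- L = 4, r = 0.8: SE = √[(0.90 + 0.85)/30] = 0.242; 0.15/0.242 = 0.62; false positives 9.4% (noncentral t, 58 df).
- L = 8, r = 0.5: SE = √[(0.75 + 0.5625)/30] = 0.209; 0.225/0.209 = 1.08; false positives 18.5%.

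| Comparison | Simulated false positives |
|---|---|
| Unmatched, same two loci painful in all cases | 9.4-18.1% |
| Unmatched, warm loci favoured 3:1 | 5.4-6.3% |
| Unmatched, pain spread evenly | 4.6-5.4% |
| Matched loci, all 18 settings | 4.5-5.4% |
| Any of L separate locus tests, uncorrected | 12.2-25.6% |

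The first row depends heavily on the assumed offset: 5-6% at 0.1 SD, 7-11% at 0.2 SD and 18-43% at 0.5 SD.

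**Power and precision.** For 0.8 SD warming at the painful loci, matched loci give 89-97%. The all-loci mean sees only 0.8 × 2/L = 0.40, 0.27 or 0.20 SD, and its power is 13-49%. With the same loci painful in all cases, matched power falls to 52-59% at 0.5 SD and 23-26% at 0.3 SD. With r = 0.8 the matched 95% CI half-width is 2.00 × √(2 × 0.90/30) = 0.49 SD; over all settings it is 0.42-0.49 SD.

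**Which temperature.** Raw values keep any room or body temperature difference between groups. Suppose a shift of 0.3 SD between groups. Then 0.3/√(2 × 0.75/30) = 1.34 and 0.3/√(2 × 0.90/30) = 1.22, which give 26% and 23% false positives at matched loci (up to 28% when painful loci vary). A clean outside reference removes the shift and has 94% to over 99% power at 0.8 SD. If the reference itself warms by 0.4 SD, power is 42-79%, against 89-94% unsubtracted. Neither measure is better in every case.

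**Standard error.** If each case's difference from the control mean is analysed as a one-sample interval, control variability is left out. With equal variances the SE is too small by a factor of √2: 2.045/√2 = 1.45, or about 15-16% false positives (12-17% across settings).

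**The case against.** Several points on the other side stand.

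- The natural reading of 3.1 is the same anatomy in controls, and 12.1 B already provides it. The loci may be listed on the data collection form, which is not in the public text; part of section 16 is also absent. This makes the fix easy, but neither 3.1 nor 19.1 makes the link.
- A reader might infer that the plan describes an unmasked, biased reading. It does not. Readings precede swab contact (12.1 A), so swab pain cannot affect acquisition, and analysis is off-visit on de-identified data in a separate laboratory (12.1 C, 14.1). De-identification does not by itself hide group or pain score, so these steps do not establish masking.
- A reader might infer that an analyst will choose the subtraction that gives the best result. With the choice made after seeing results, three options would give 7-14% false positives and five would give 9-21%. The stated purpose is visibility, however, so the options may be for display only, with no effect on the endpoint.
- Setting metrics after data collection concerns diagnostic rules. It need not apply to the 3.1 endpoint.
- Point loci do not describe region and size. The free marking should therefore stay, for the pain maps.

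**Conclusion.** The concern holds as a cheap improvement. The text leaves the control region and the endpoint temperature open, and it states no masking or lock of the reading. The direction of the risk follows from the documents; its size does not. The excess in false positives is little or none if painful loci vary between women (about 5-6%), and 9-18% only in the extreme where the same two loci, assumed 0.3 SD warmer, hurt in every case.

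It would go too far to say that no case-control difference could be interpreted, or that the reading will be biased. The consequence is a pilot estimate that may be biased or unrepeatable. Even with the fix, 30 per group supports an estimate with a CI, not a firm test: the half-width is 0.42-0.49 SD under the assumed inputs.

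**What to change.** 1. **Section 3.1.** List the loci and fix in advance the swab score that counts as painful. Take each case's mean temperature at her painful loci. Take each control's mean over the same loci, weighted by how often each is painful in cases. Report one difference with a 95% CI whose standard error includes both case and control variability: √(s²cases/n + s²controls/n), Welch or equivalent. Do not use the all-loci mean or uncorrected tests per locus.
2. **Section 19.1.** Before any linkage, fix one temperature measure computed from the extracted raw data: either raw, or raw minus one pre-specified reference outside the affected field. Report the other as a sensitivity analysis. Keep free marking and other subtractions for the pain maps and display.
3. **Reading.** Have existing laboratory staff or co-investigators extract and lock temperatures at all loci from the coded images, by a written landmark rule, before group and swab scores are linked. State that masking may be incomplete: the camera "software stores both of these images along with metadata in a single jpeg", so visible signs may reveal status.

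Cost: protocol wording, a landmark rule and, with an assumed 4-8 loci, 60 × 4 = 240 to 60 × 8 = 480 placements. No extra visit or participant is needed. Section 20.3 limits data access to the PI and co-investigators, so access for laboratory staff may need clarifying. Downsides are less freedom to tune images and possible missed warm spots between loci.

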12.0 Procedures Involved*

12.1 Provide a description of **all research procedures or activities** being performed and when they are performed once a subject is screened and determined to be eligible. Provide as much detail as possible.

NOTE: This should serve as a blueprint for your study and include enough detail so that another investigator could pick up your protocol and replicate the research. For studies that have multiple or complex visits or procedures, consider the addition of a schedule of events table in in your response.

Response:

All procedures will be performed on the same day as screening and consent and are expected to take 30-60 minutes. An annotated pain map of the vulva will be created based on subjective assessment of pain, and thermographic imaging.

- A. Images and Thermographic readings will be taken with an infrared camera prior to any physical contact with the vulva of the patient other than by placing a calibrated paper drape circumferentially on the vulva outside of the area of interest. The drape will be calibrated to maintain pain map/image size comparison between patients.
- B. Subjective pain at several predetermined loci will be assessed with a cotton swab (standard of care) and rated on a Likert scale of 0-10. This data will be added to the thermographic map.
- C. Comparative analysis of the two measures will be performed (separate from visit). Patient demographic and health data (see table below) will be collected by direct participant interview and review of the patient's chart in Allscripts.

12.2 Describe what data will be collected.

NOTE: For studies with multiple data collection points or long-term follow up, consider the addition of a schedule or table in your response.

Response:

Patient Name

DOB

MR#

Date of Visit

Vulvar images, both plain and infrared.

Pain sensitivity data on a Likert scale of 0-10 using cotton-tipped swabs.

Status (PWD or Control)

Race

Gravida

Para

Vaginal Births

Cesarean Births

Sexually Active

Dyspareunia

Smoking

Marital Status

Education Level

Medical History

Depression

Anxiety

Fibromyalgia

Chronic Pelvic Pain

Interstitial Cystitis

Endometriosis

Irritable Bowel Syndrome

TMJ

Other

h/o yeast infections

h/o BV

h/o abuse

PWD Patients Only

Symptom Duration

Pain Map Score

Pain Diary Score

FSDS

Previous Rx (Y/N)

Previous Rx (type)

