20.5 A. *How will the data be transported?*

Response:

On a password-protected, HIPAA-compliant flash drive.

B. Confidentiality of Study Specimens

Describe the local procedures for maintenance of confidentiality of study specimens.

N/A: No specimens will be collected or analyzed in this research.
(Skip to Section 21.0)

20.6 B. Where and how will all specimens be stored? Include information about: physical controls, authorization of access, and labeling of specimens, as applicable.

Response:

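### The endpoint and hypothesis name inflammation, but the plan collects no independent or scored measure of it, so the data can support a conclusion about temperature only

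*Combined protocol and SAP*

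**What the plan says.** The only endpoint, in Section 3.1, is "Thermographic evidence of inflammation in the areas of pain sensitivity in women with provoked vulvodynia compared to normal controls". The hypothesis in 2.2 reads: "Women with vulvodynia will show specific patterns of pain sensitivity and inflammatory changes (identified by thermography) compared to women without vulvar pain". Section 2.1 says the technique will "simultaneously use thermal and photo imaging to identify regions of inflammation". It is more guarded a little later: "we will assess thermal indicators of inflammation with an infrared camera and subjective pain sensitivity with traditional methods".

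The physical measurements in 12.2 are "Vulvar images, both plain and infrared" and "Pain sensitivity data on a Likert scale of 0-10 using cotton-tipped swabs". The rest of that list is identifiers, demographic and obstetric items, medical history and, for cases, symptom duration, pain and sexual-distress scores and previous treatment. Part B of Section 20 carries the line "No specimens will be collected or analyzed in this research". The tick mark beside it cannot be seen, but the specimen questions that follow are blank and 12.2 lists no specimen.

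Section 19.1 says that raw temperatures will be extracted from the image files. Pressure, temperature and colour are then to be related to a positive diagnosis. Inflammation is not mentioned in that section.

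**The concern.** Going from a temperature pattern to inflammation is an inference, and nothing in the study tests it. A warm site may be warm for another reason, and a site at normal temperature may still be inflamed. Without a reference measure in the same women, the study cannot estimate how well temperature tracks inflammation. Nor does the background in 4.1 state an accuracy figure or a validation from elsewhere.

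What is at stake is the headline conclusion. A group difference would be written up as inflammation in vulvodynia, because that is what the endpoint says. The absence of a difference could be written up as absence of inflammation. Section 19.1 encourages the second reading by asserting that the camera will reveal any link between temperature and the condition.

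**Working it through.** The plan gives no figure to reproduce. It states 60 women, 30 per group (Section 1.0), and declines a power analysis (19.2). The main check sets the sections side by side.

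| Element | Where | What it refers to |
|---|---|---|
| Endpoint | 3.1 | Inflammation, by thermography |
| Hypothesis | 2.2 | Pain patterns and inflammatory change, by thermography |
| Data | 12.2 | Plain and infrared images, swab pain score, history |
| Specimens | 20, part B | None |
| Analysis | 19.1 | Pressure, temperature and colour against diagnosis |

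The first two rows need a link from temperature to inflammation. None of the other three supplies it. Colour from the photographs could be a second indicator, but no section says how it is scored or when it counts as inflammation.

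The arithmetic below is illustration only. Every prevalence, sensitivity and specificity is assumed, as is the two-sided 0.05 level. Splitting women into warm and not warm is also my simplification, because the plan sets no threshold.

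- Proportion warm in a group: p = π·Se + (1 − π)(1 − Sp), where π is the proportion inflamed.
- Power for two proportions, n = 30 per group: Φ{[p₁ − p₂ − 1.96√(2p̄(1 − p̄)/n)] / √[(p₁(1 − p₁) + p₂(1 − p₂))/n]}.

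**A. No woman is inflamed (π = 0).** Non-inflammatory warmth is assumed in 10% of controls and in 30%, 40% or 50% of cases. For 40% v 10%, p̄ = 0.25 and the power is Φ{(0.30 − 1.96 × 0.1118)/0.1049} = Φ(0.77) = 78%. For 30% and 50% it is 49% and 94%. These are the chances of a significant difference with no inflammation present.

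**B. Half the cases and 5% of controls are inflamed, Sp = 90% in both groups.**

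| Se | Warm, cases | Warm, controls | Power |
|---|---|---|---|
| 30% | 0.5×0.3 + 0.5×0.1 = 20% | 0.05×0.3 + 0.95×0.1 = 11% | 16% |
| 50% | 30% | 12% | 40% |
| 80% | 45% | 13.5% | 78% |
| 90% | 50% | 14% | 87% |

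So inflammation in half the cases could well give a null result if temperature is an insensitive proxy.

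**A and B together.** Scenario A at 30% v 10% expects 9 warm cases and 3 warm controls. Scenario B at Se 50% expects 9 and 3.6. One has no inflammation and the other has it in half the cases, yet the data are practically the same. Only a measure of inflammation other than temperature could separate them.

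**Temperature itself.** Power for a difference of d SDs is Φ(d√(n/2) − 1.96). At d = 0.5 this is Φ(1.936 − 1.960) = 49%, and at d = 0.3 it is 21%. The difference detectable with 80% power is (1.960 + 0.842) × √(2/30) = 0.72 SD. A null result would therefore not exclude a moderate thermal difference, and still less exclude inflammation.

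**The case against.** The strongest defence is that the plan already speaks of a proxy. The endpoint is thermographic evidence, and Sections 2.1 and 4.1 refer to thermal indicators. The plan also removes some rival causes of warmth:

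- Other vulvar or vaginal disorders are excluded (8.2, 10.1), and for controls Section 5.1 gives interference with the thermal map as the reason.
- Conditions that may affect the outcome are excluded (19.3).
- Previously diagnosed cases are untreated when assessed (5.1).
- Images are taken before any contact with the vulva other than placing the drape (12.1).

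In addition, this is a declared pilot. The primary objective (pain maps correlated with co-morbidities) and the diagnostic analysis in 19.1 do not need inflammation to be shown.

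Much of this stands. It limits the consequence and makes a positive result more suggestive. It does not supply the missing link, because 2.2 says without qualification that thermography identifies the inflammatory change. Pilot status explains the absent power analysis. It does not justify an endpoint that the data cannot verify.

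Four stronger readings are tempting, and the documents do not support them:

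- *Temperature is the only thing measured.* Photographs are taken, 2.1 names photo imaging as a means of finding inflammation, and 19.1 uses colour.
- *Cooler painful sites go unmarked.* Section 19.1 mentions marking thermal increases but does not restrict marking to them. A painful site is marked for its pain, and raw temperatures are extracted whatever their direction.
- *A given share of women would be wrongly labelled inflamed.* The study labels no individual woman as inflamed. The individual probability in 19.1 concerns the diagnosis.
- *The proxy is invalid.* The documents state no validation, which is a weaker point. The cited review of proinflammatory mediators and the attached data collection form were not available to check.

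**Conclusion.** The point holds in a limited form. As planned, the study can support or fail to support a thermal difference between cases and controls. It cannot attribute such a difference to inflammation, and it cannot exclude inflammation if no difference is seen. It would go too far to say that no result could be informative, since a positive finding would be real evidence of a thermal difference and could fairly be called consistent with inflammation.

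The documents do not allow the size of the problem to be fixed. The scenario figures (49% to 94% chance of a significant result without inflammation, 16% to 87% power with it) show only that both errors are plausible at 30 per group under the stated assumptions. The conclusion itself does not depend on them. It rests on 2.2, 3.1, 12.2 and 19.1 as written, and on the unseen data collection form adding no measure of inflammation beyond 12.2.

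This should be corrected, but it does not undermine the pain-map objective or the analysis against diagnosis.

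**What to change.** - **3.1:** restate the endpoint as the difference in vulvar surface temperature at the predetermined loci (signed, two-sided), cases v controls, and its relation to the pain rating. Take it from the raw temperatures that 19.1 already extracts. Using the predetermined loci also gives controls, who may have no painful area, the same sites as cases. Because 19.1 offers several ways of subtracting body temperature, name one for this endpoint in advance.
- **2.2:** replace the reference to inflammatory change identified by thermography with temperature patterns.
- **Interpretation, in 3.1 or 19.1:** add that a thermal difference will be reported as such and described at most as consistent with inflammation, and that absence of a difference will not be reported as absence of inflammation.

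If the investigators want to keep an inflammation endpoint, they would need either a stated justification of the proxy or an independent measure. A prespecified scoring rule for the photographs already taken would add a second indicator without a new procedure, though it too would need support as a measure of inflammation.

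The main fix needs no extra visit, subject or procedure. Its cost is a more modest headline claim.
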